## **6.7 Values Below LLQ**

Concentrations for TTP488 or metabolites below the lower limit of quantification (LLQ) for the assay will be set to zero, for the purpose of analysis.

## **7 Analysis Deviations**

All statistical analyses and summary information will be generated according to this analysis plan. Any deviation from this plan will be documented in the clinical study report. Exploratory analyses are permitted per protocol; those analyses will not be considered to be deviations.

## **8 Software**

All analyses will be done using SAS Version 9.3 or later.

## 9 Data Displays

The plans for displaying data will conform to this guideline and also to ICH E3 (*Structure and Content of clinical Study Reports*), and to ICH E9 (*Statistical Principles for Clinical Trials*).

The following excerpt from ICH E3 (1996) applies to this SAP:

“The guidance provided below is detailed and is intended to notify the applicant of virtually all of the information that should routinely be provided so that post-submission requests for further data clarification and analyses can be reduced as much as possible. Nonetheless, specific requirements for data presentation and/or analysis may depend on specific situations, may evolve over time, may vary from drug class to drug class, may differ among regions and cannot be described in general terms; it is therefore important to refer to specific clinical guidelines and to discuss data presentation and analyses with the reviewing authority, whenever possible. Detailed written guidance on statistical approaches is available from some authorities.

“Each report should consider all of the topics described (unless clearly not relevant) although the specific sequence and grouping of topics may be changed if alternatives are more logical for a particular study” (p. 2).

In accordance with FDA and ICH guidance, tables, figures, and key data listings are planned. Exploratory and data-driven data displays may also be generated.

Planned displays will include, but are not limited to, the following:

- Summary of Accountability (number screened, enrolled, completing, withdrawn, by reason; listing of withdrawals with study day and reason)
- Summary of Demography and Background Data
- Summary of Adverse Events
- Summary of Adverse Events by severity and by relatedness
- Summary of Vital Signs (change over time; criteria of potential clinical concern)
- Summary of Laboratory Data, including LFTs (change over time, TEAV, and criteria of potential clinical concern)
- Summary of PK Data
- Summary of Plasma Amyloid-beta Data
- Summary of Efficacy Data (ADAS-cog, CDR-sb, CDR-global, MMSE, ADCS-ADL, NPI)
- Summary of MRI Data
- Summary of PET Data
- Listing of Demography
- Listing of Dosing
- Listing of all Adverse Events
- Listing of all Adverse Events that resulted in Death
- Listing of all Serious Adverse Events
- Listing of all Adverse Events resulting in Study Termination

- Listing of Treatment-emergent Abnormal Values of Potential Clinical Concern for Clinical Laboratory Data
- Listing of Vital Signs Data
- Listing of QTc data that meet criteria of potential concern as described in ICH E14
- Listing of Concentration Data
- Listing of MRI safety Data
- Listing of MRI volumetric Data
- Listing of FDG-PET SUVR Data

In addition to the data summaries and listings described above, the set of displays will include clinical laboratory normal ranges (with units) and also a display of the MedDRA mapping glossary, which will display the verbatim text as reported by the investigator, the LLT, PT, and SOC.

## 10 Values of Potential Clinical Concern

Parameter	Threshold (study-specific threshold calculated)
Hematology	
Hemoglobin	<8.5 g/dL
Hematocrit	<25 %
WBC (Leukocytes)	<0.6 x LLN (<2.1 10  /uL)
Platelets	<0.5 x LLN (<70 10  /uL)
Total Neutrophils (Abs)	<0.8 x LLN (<0.8 10  /uL)
Lymphocytes (Abs)	<0.6 x LLN (<0.6 10  /uL)
Chemistry	
Total bilirubin	>2.5 x ULN (>2.7 mg/dL)
AST	>3 x ULN (>102 U/L)
ALT	>3 x ULN (>123 U/L)
Alk Phosphatase	>3 x ULN (>348 U/L)
Creatinine	>2 mg/dL
BUN	>1.4 x ULN (30.8 mg/dL)
Glucose	≤70 mg/dL or ≥270 mg/dL
Uric acid	>12 mg/dL
Sodium	<125 mmol/L or >155mmol/L
Potassium	<3.0 mmol/L or >6.0 mmol/L
Bicarbonate	<16 mmol/L
Calcium	<6.0 mg/dL and >13.0 mg/dL
Triglycerides	>750 mg/dL
Electrocardiogram	
Heart Rate	<50 bpm and ≥/=25% decrease from baseline >100 bpm and ≥/=25% increase from baseline
PR interval	≥200 msec and ≥25% increase from baseline
QRS interval	≥200 msec and ≥25% increase from baseline
QTc interval	≥500 msec ≥30-60 msec increase >60 msec increase
Vitals (sitting)	
SBP	≥190 mmHg (entry is <180 mmHg) Systolic <80 mm Hg Decrease from baseline ≥30 mmHg
DBP	≥120 mmHg (entry is <105) <50 mm Hg

Parameters not provided with specific thresholds for clinical concern: RBC count, eosinophils, basophils, monocytes, direct or indirect bilirubin (just total as shown above), chloride, albumin, total protein, insulin, total cholesterol, HDL, LDL, urinalysis, pulse rate from VS (rely on ECG heart rate).

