7. MRI consistent with a diagnosis of probable Alzheimer's disease. A head CT scan may be used for evaluation if there is a documented contraindication to an MRI (e.g. pacemaker).
8. Mini-Mental State Exam (MMSE) score of 21-26 inclusive at screening.
9. CDR global score of 0.5 or 1 at screening.
10. Rosen-Modified Hachinski Ischemia Score ≤ 4 at screening.
11. Participants must be on a stable dose of a background cholinesterase inhibitor and/or memantine (approved by the relevant health authority where the trial is being conducted) at least 3 months prior to randomization and must agree not to change the dose during the study period unless the investigator judges that the dose needs to be reduced or stopped due to a safety and/or tolerability reason.
12. No clinically significant, (in the opinion of the investigator) laboratory abnormalities at screening. If the results of clinical laboratory testing are outside normal reference ranges, the subject may be enrolled but only if these findings are determined to be not clinically significant by the investigator. This determination must be recorded in the subject's source documents. A summary of values of potential clinical concern is provided in [APPENDIX 1](#).
13. Subject must be able to ingest oral medications.

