
APPENDICES

APPENDIX 1

CRITERIA FOR SAFETY VALUES OF POTENTIAL CLINICAL CONCERN

Criteria for Safety Values of Potential Clinical Concern

Hematology

Assay	Lower limit of the normal reference range (LLN)	Upper limit of the normal reference range (ULN)
Hemoglobin	<0.8 times	>1.2 times
Hematocrit	<0.8 times	>1.2 times
RBC	<0.8 times	
Platelets	<0.5 times	>1.75 times
WBC	<0.6 times	>1.5 times
Total Neutrophils (abs)	<0.8 times	>1.2 times
Eosinophils (abs)		>1.2 times
Monocytes (abs)		>1.2 times
Basophils (abs)		>1.2 times
Lymphocytes (abs)	<0.8 times	>1.2 times

Chemistry

Assay	Lower limit of the normal reference range (LLN)	Upper limit of the normal reference range (ULN)
Total bilirubin		>1.5 times
AST		>3 times
ALT		>3 times
GGT		>3.0 times
Alkaline Phosphatase		>3.0 times
Creatinine		>1.5 times
BUN		>1.3 times
Glucose	<0.6 times	>1.5 times
Uric acid		>1.5 times
Sodium	<0.95 times	>1.05 times
Potassium	<0.9 times	>1.1 times
Calcium	<0.9 times	>1.1 times
Albumin	<0.8 times	>1.2 times
Total protein	<0.8 times	>1.2 times
Bicarbonate	<0.9 times	>1.1 times
Chloride	<0.9 times	>1.1 times

APPENDIX 2

PROHIBITED MEDICATION LIST

Prohibited Medication List

The following medications are NOT ALLOWED as concomitant medications during the study. The list is not exhaustive and therefore, the Investigator is asked to contact the Medical Monitor and/or the Sponsor for clarification regarding the acceptability of similar agents not mentioned here.

Drugs known to be strong CYP 2C8 inhibitors: NOT ALLOWED
gemfibrozil
clopidogrel

Flockhart DA. Drug Interactions: Cytochrome P450 Drug Interaction Table. Indiana University School of Medicine (2007). "<http://medicine.iupui.edu/clinpharm/ddis/clinical-table/>" Accessed 17 Nov 2017.

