## 1.9 Modifications from the Statistical Section of the Protocol

One modification from the Statistical Section of the Protocol is reflected in this SAP, based on agreement with the Neurology Products Division of the FDA:

- (1) Elimination of the use of Bazett's correction for QT-interval analysis, based on the recommendation depicted in ICH E14 Q&A R3 (dated 10 December 2015).

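### The calcium flag in SAP Section 10 joins its two limits with *and*, so no value can meet it; the connector should be *or*, and a few other entries in the table need reconciling

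*SAP*

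**What the plan says.** SAP 4.2.4 defines a treatment-emergent laboratory value of potential clinical concern by reference to Section 10 of the SAP. SAP 5.4.3 (laboratory) and 5.4.2 (vital signs) flag subjects against the same table and compare proportions between treatment groups. SAP Section 9 plans the matching laboratory summary and listing.

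In that table the calcium row is "<6.0 mg/dL and >13.0 mg/dL". Other two-sided laboratory rows are built differently: sodium is "<125 mmol/L or >155mmol/L" and potassium is "<3.0 mmol/L or >6.0 mmol/L". Glucose also uses *or*.

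The protocol has its own table in Appendix 1, headed "CRITERIA FOR SAFETY VALUES OF POTENTIAL CLINICAL CONCERN". The protocol body points to it in inclusion criterion 12, on screening laboratory results: "A summary of values of potential clinical concern is provided in" that appendix. Protocol 9.6.1.3, which lists the laboratory analysis variables, plans proportions with clinically significant values but neither gives limits nor cites Appendix 1. Protocol 9.0 says the SAP takes precedence over the protocol.

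On departures from the protocol, SAP 1.9 says "One modification from the Statistical Section of the Protocol is reflected in this SAP", namely dropping Bazett's correction.

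**The concern.** The proportion of subjects flagged, by arm, is a reported safety result. A rule that cannot be met returns zero in each arm, and in a table of counts that zero looks like a clean finding. Nothing in the output would show that the rule was empty.

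The other mismatches in Section 10 suggest that the table was not checked line by line against this protocol. There are also two tables with nearly the same name and different limits, and no sentence relates one to the other. A reader of the study report could reasonably ask which was used.

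**Working it through.** **1. The calcium rule.** The set of values below 6.0 and also above 13.0 mg/dL is empty. On a grid from 0 to 25 mg/dL in steps of 0.1 (251 values), *and* flags 0 and *or* flags 180. The 180 shows only that the corrected rule is not empty; it is not an expected rate.

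**2. How *and* is used elsewhere in the table.** In the heart rate, PR and QRS rows, *and* is a true joint condition: an absolute limit plus a change of at least 25% from baseline. A programmer who gives the word the same meaning throughout obtains the empty calcium rule.

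**3. Section 10 against Appendix 1.** Appendix 1 has 26 analytes and Section 10 has 19 laboratory analytes; 18 are shared. Of these:
- 3 are identical: AST, ALT, alkaline phosphatase.
- 3 keep the lower multiple and drop the upper limit: WBC, platelets, neutrophils.
- 3 change the multiple: total bilirubin, BUN and lymphocytes (lymphocytes also lose the upper limit).
- 9 change from a multiple to an absolute value: hemoglobin, hematocrit, creatinine, glucose, uric acid, sodium, potassium, bicarbonate, calcium.

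So 3 + 3 + 9 = 15 of 18 differ in form or value.

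**4. Size of the differences.** The documents give no reference ranges, so the bracketed SAP values cannot be reproduced independently. The reference limit can only be worked back as threshold divided by multiple:
- Bilirubin, SAP ">2.5 x ULN (>2.7 mg/dL": 2.7 / 2.5 = 1.08 mg/dL. The Appendix 1 limit is then 1.5 x 1.08 = 1.62 mg/dL. Rounding of 2.7 (2.65 to 2.75) gives 1.59 to 1.65.
- BUN, SAP ">1.4 x ULN (30.8 mg/dL": 30.8 / 1.4 = 22.0 mg/dL. Appendix 1: 1.3 x 22.0 = 28.6 mg/dL.
- Lymphocytes: 0.6 / 0.6 = 1.0 x10^3/uL. Appendix 1: 0.8 x 1.0 = 0.8, against 0.6 in the SAP.

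Not every change lowers the count. For low glucose the SAP flags 70 mg/dL or less and Appendix 1 flags below 0.6 x LLN. Appendix 1 would reach higher only if LLN exceeded 70 / 0.6 = 116.7 mg/dL. Assuming an LLN of 60 to 75, its cut-off is 36 to 45, and the SAP flags more.

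**5. Other entries in Section 10.**

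| Entry in Section 10 | Set against |
|---|---|
| Vital signs headed as sitting | Supine in protocol 7.1.1 and in the SAP's own schedule (Section 12) |
| Entry limits of systolic <180 and diastolic <105 | Exclusion criterion 12: systolic >=160 or diastolic >=100 excluded |
| QTc >=500 msec | >500 msec in SAP 5.4.5 |
| GGT: no limit, and not in the closing list of parameters left without one | On the SAP 4.2.4 analyte list; 3 x ULN in Appendix 1 |
| Triglycerides: a limit | In neither document's analyte list |

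Eight analytes have an Appendix 1 limit and no Section 10 limit. The closing list names seven of them; GGT is the exception.

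**The case against.** The best defence is that the calcium row simply lists two limits and that any competent programmer would read it as *or*. The three parallel laboratory rows support this, and in the ECG rows the joint *and* is set in bold while the calcium one is not. This stands to the extent that a reported count of zero is not certain. It depends on literal programming. A marked calcium abnormality would also not vanish from the report: SAP 4.2.4 counts shifts from normal to abnormal, and SAP 5.4.3 gives the minimum and maximum at each assessment time and has potentially significant abnormalities reported as adverse events. None of this is a reason to leave an unmeetable rule in a final SAP.

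Three stronger readings are tempting, and the documents do not support them.

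- *A reader might infer that flag counts depend on which document is used.* They do not. The SAP supersedes the protocol, and SAP 4.2.4, 5.4.2 and 5.4.3 all name Section 10. Appendix 1 is cited for screening eligibility, and the protocol's statistical section never adopts it for reported proportions. A different limit is not a wrong count.
- *A reader might infer that SAP 1.9 is false because it declares one change only.* It speaks of the protocol's statistical section, and Appendix 1 lies outside that section.
- *A reader might infer that the bilirubin flag above 2.5 x ULN contradicts the 2 x ULN in SAP 5.4.4.* The latter is one part of a composite liver rule that also requires AST or ALT of at least 3 x ULN. Subjects meeting it are listed whatever the stand-alone flag says.

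**Conclusion.** The calcium criterion is wrong as written. Programmed literally, it yields zero flags in each arm for any data. That rests on logic alone and needs no assumption about reference ranges; whether the reported count would in fact be zero depends on how the row is coded.

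The mismatches in vital-sign position, blood pressure entry limits, QTc boundary and GGT are real but minor, and none is shown to change a conclusion. The differences from Appendix 1 are a matter of clarity. The bilirubin, BUN and lymphocyte comparisons rest on reference limits worked back from the SAP's bracketed values. No view is taken here on which clinical limits are right.

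This is a small safety-reporting correction with no bearing on alpha, power or the co-primary analyses.

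**What to change.** - In the calcium row of SAP Section 10, change *and* to *or*, matching glucose, sodium and potassium.
- Reconcile the vital-sign heading with supine measurement, the quoted blood pressure entry limits with exclusion criterion 12, and the QTc boundary with SAP 5.4.5.
- Either give GGT a limit or add it to the closing list of parameters without one. Check whether the triglycerides row belongs, since neither document lists that analyte.
- Add one sentence: Section 10, not protocol Appendix 1, defines values of potential clinical concern for analysis.

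Tabulating flags against both tables is unnecessary. The cost is a few lines of SAP text and a check that the flag programs match. No additional data or tables are needed.

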12. Participants with poorly controlled hypertension with or without existing therapy (systolic ≥ 160 or diastolic ≥ 100). Subjects will be allowed to participate with management of blood pressure below the exclusionary levels with introduction of an allowable medication and the subject has been on the drug for 4 weeks prior to baseline.
13. Participants with evidence or history of severe drug allergies (such as resulting in dyspnea or severe rash) or allergy to any constituents of the study drug as formulated.
14. Known history of alcohol or drug abuse or dependence (as defined by the DSM-IV-TR) within 5 years prior to dosing or a positive result on the drug screening test (unless due to a permitted concomitant medication (i.e., a benzodiazepine as a sleep aid).
15. Patients with pulmonary hypertension are excluded.
16. Any contraindications to the MRI procedure based on local operating procedures and instructions (e.g., clinically significant claustrophobia, non-removable ferromagnetic implants). It is acceptable to premedicate patients per usual local practice provided this medication is not administered within 5 half-lives preceding any efficacy assessments. Patients with contraindications to MRI (ex: pacemakers) may undergo computed tomography (CT) on approval by Sponsor.
17. Any contraindications to the FDG-PET study (e.g. allergy to any component of the FDG dose) in the mild AD dementia subject cohort undergoing a PET scan.
18. Previous exposure to investigational therapies for Alzheimer's disease that are being investigated for possible disease modification activity (e.g., azeliragon, passive immunotherapies and secretase inhibitors) within 4 months of screening for the current protocol. Subjects who were exposed to vaccine therapy or other active immunization (if they were randomized to active treatment) will not be allowed in the trial. Previous exposure to any other investigational drug as part of a clinical trial, including investigational therapies

for Alzheimer's disease that are being investigated for non-disease modifying purposes, within 60 days or 5 half-lives whichever is longer, prior to screening.

19. Participants who are taking or are expected to use drugs known to be strong CYP2C8 inhibitors or (See [APPENDIX 2](#) for a list of such medications).

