9.6.1.2 Vital Signs

Vital signs measures of blood pressure and pulse will include the following variables of analysis:

- Mean values and mean changes of values from Baseline to Visit

- Proportions of subjects with clinically significant abnormal values or changes in vital signs measures.
- Proportions of subjects with AEs related to vital signs

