#### 4.2.3 Vital Signs

Vital signs measurements consist of blood pressure and pulse rate. Variables of analysis will include means, mean changes over time, and proportions of subjects meeting criteria for potential clinical concern in vital signs:

- Mean and mean changes in systolic and diastolic blood pressures
- Mean and mean changes in pulse
- Proportions of subjects with treatment-emergent values or changes of potential clinical concern.

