#### **5.4.2 Vital Signs**

Subjects with vital signs meeting the criteria in [Section 10](#) of this SAP for values of potential clinical concern will be flagged and summarized. Proportions of subjects with vital signs of potential clinical concern will be examined for the treatment groups.

No formal inferential statistics will be applied to the vital signs data.

For each post-Baseline assessment, descriptive statistics are provided for the assessment value and the change from Baseline to the assessment with mean, median, standard deviation, minimum, and maximum at each assessment time.

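### SAP Section 10 sets its high blood-pressure flags beside entry limits that differ from protocol exclusion 12, and flags a systolic fall of 30 mmHg but no rise

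*SAP*

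**What the plan says.** The vital-signs block of SAP Section 10 is labelled as sitting. Its high systolic criterion reads "≥190 mmHg (entry is <180 mmHg" and its high diastolic criterion reads "≥120 mmHg (entry is <105". The only change criterion for systolic pressure is "Decrease from baseline ≥30 mmHg". Diastolic pressure has no change criterion in either direction.

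Protocol Section 4.2, exclusion 12, removes patients with "poorly controlled hypertension with or without existing therapy (systolic ≥ 160 or diastolic ≥ 100" mmHg. The allowance for newly treated hypertension does not raise that ceiling: "Subjects will be allowed to participate with management of blood pressure below the exclusionary levels". Protocol Section 7.1.1 and the schedules in both documents have blood pressure taken supine.

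The flags feed a planned comparison. SAP Section 4.2.3 names as a variable "Proportions of subjects with treatment-emergent values or changes of potential clinical concern", and protocol Section 9.6.1.2 names "Proportions of subjects with clinically significant abnormal values or changes in vital signs measures". SAP Section 5.4.2 says: "Proportions of subjects with vital signs of potential clinical concern will be examined for the treatment groups". The same section rules out inferential tests on vital signs and adds descriptive statistics by visit. SAP Section 1.9 declares one departure from the protocol's statistical section, the dropping of Bazett's correction.

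**The concern.** The entry limits printed beside the flags are not those in the protocol. Whoever reads the table will believe that a flagged systolic value lies just above what was allowed at entry, when it lies three times as far above (30 against 10 mmHg).

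The lack of a rise criterion is a separate gap. Both documents promise proportions with abnormal values or changes and neither restricts the direction, yet the table counts only falls. Section 10 flags ECG heart rate in both directions, so the one-sided systolic rule is not a general convention of the table, and no reason is given for it.

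At stake is the one planned between-arm summary that counts individual blood-pressure outliers. Visit means can conceal a subset of patients with large rises, and a proportion of flagged patients is meant to show such a subset.

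**Working it through.** The inputs are the flags and bracketed entry limits in SAP Section 10, and exclusion 12 in protocol Section 4.2. No sample-size, power or alpha figure is involved.

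**Gap from entry limit to high flag (flag minus limit)**

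| | SAP's stated limit | Protocol's limit |
|---|---|---|
| Systolic | 190 − 180 = 10 mmHg | 190 − 160 = 30 mmHg |
| Diastolic | 120 − 105 = 15 mmHg | 120 − 100 = 20 mmHg |

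**Smallest rise that reaches the flag, from the highest admissible whole-mmHg baseline**

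- Systolic: 190 − 179 = 11 under the SAP's limit; 190 − 159 = 31 under the protocol's.
- Diastolic: 120 − 104 = 16 under the SAP's limit; 120 − 99 = 21 under the protocol's.
- From lower systolic baselines the rise needed is 40 (from 150), 50 (from 140) or 60 (from 130).

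**Does a 30 mmHg systolic rise meet any flag?** If baseline is below 160, baseline + 30 is below 190. The highest value reached is 159 + 30 = 189, so the high flag is not met from any admissible baseline, and no change flag covers a rise. Under the SAP's stated limit of 180, the same rise would be flagged from baselines of 160 to 179. That partial cover disappears under the protocol's limit. A 30 mmHg fall is flagged from every baseline.

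This step needs no assumption about the distribution of blood pressure. It needs only that the baseline used in analysis meets exclusion 12.

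**How often would the systolic flag fire?** The documents give no mean or standard deviation for blood pressure, so this can only be illustrated on assumed inputs.

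- Correlated visits: usual systolic mean 130–140, between-patient SD 10–14, within-patient SD 8–12, six treatment visits, drug shift 0 or +5 mmHg, screening and baseline both below 160. By simulation, about 0 to 2.7 patients per 400 ever reach 190. About 9 to 111 per 400 have a rise of 30 or more at some visit, and 97.6% to 100% of those never reach 190.
- Independent visits, as an upper bound: normal readings with mean 130–140 and SD 14–20. The chance of 190 or more is about 0.001% to 0.6% per reading. Over six visits that is about 0.02 to 15 patients per 400.

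The spread between these results shows how far the answer depends on the assumptions.

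**The case against.** The strongest reply is that the flags are absolute values. The bracketed entry limits enter no calculation, so correcting them, or the posture label, changes no patient's status. Nothing in Section 10 says that the flags were derived as the entry limit plus a margin. This stands. The wrong limits do not cause the missing rise criterion, and correcting them would not supply it.

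Nor is a 30 mmHg rise lost to the analysis. It contributes to the by-visit change summaries, which include the maximum (SAP Section 5.4.2). The protocol plans minimum and maximum values with change from baseline (Section 9.6.2) and proportions with adverse events related to vital signs (Section 9.6.1.2). SAP Section 4.2 has medically qualified staff review the vital-signs listings and has untoward findings reported as adverse events. This also stands. The gap is confined to the flagged proportions.

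A third reply is that no document requires change flags in both directions, and that other limits in the table are also extreme, so rarity alone is no defect. That is fair as to rarity. It does not explain why a table serving a variable of values or changes counts only one direction for systolic pressure.

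A reader might infer that the systolic flag will almost never fire. The documents do not support this as a statement of fact, because they give no blood-pressure distribution. A reader might also infer that the block was carried over from another study. The posture label and a triglyceride threshold for an analyte outside the protocol's laboratory panel are consistent with that, but neither document says so.

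**Conclusion.** Two points hold on the text alone. First, SAP Section 10 and exclusion 12 disagree on the entry limits (below 180 and 105 against below 160 and 100 mmHg), and the block's posture label disagrees with protocol Section 7.1.1. Secondly, a 30 mmHg systolic rise from any baseline meeting exclusion 12 is absent from the proportions of potential clinical concern, while a fall of the same size is counted. Rises of 31 mmHg or more can be flagged, but only from the highest baselines.

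It would go too far to say that such a rise is never counted, or that the flag proportions are the whole blood-pressure comparison, since the other summaries, listings and adverse event tables remain. The effect is limited to descriptive safety tables. No hypothesis test, alpha allocation or eligibility decision changes. Severity is minor, and the change is a cheap improvement.

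**What to change.** - Reconcile the entry limits in SAP Section 10 with protocol exclusion 12, and the posture label with protocol Section 7.1.1.
- Have the sponsor's safety physician confirm or reset the high systolic and diastolic flags against the reconciled limits, with the reason recorded. No threshold is proposed here.
- Add an increase-from-baseline systolic flag of the same size as the existing decrease flag, and report it in the same table by treatment group.

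The cost is a tracked SAP amendment, which SAP Section 1 already provides for, and reprogramming of one flag set. The downside is that more patients will be flagged, listed and reviewed. The documents do not allow the number to be computed.
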